7. RATIONALE AND BACKGROUND

Renal impairment (RI) is a common complication in patients with T2DM. In Japanese patients with T2DM, about 40% of patients have microalbuminuria or macroalbuminuria [1], and other report shows that 55% of Japanese patients with T2DM suffer from mild to moderate renal dysfunction [2].

Many of OADs are contraindicated in severe RI patients or should be carefully administered in patients with declined renal function. For biguanide, a risk of lactic acidosis increases in RI and biguanide is contraindicated in moderate or severe RI. Pioglitazone is used with no contraindication in patients with RI in USA, meanwhile in Japan it is contraindicated in severe RI patients and it requires careful administration to mild to moderate RI patients. Glinides and α -GIs also require careful administration in RI patients although the levels of severity of RI with caution are different from each drug in some measure.

The prescriptions of DPP-4 inhibitors are rapidly increasing in T2DM patients after its introduction to the Japanese clinical practice [3]. The reason of this trend might result from well-balanced drug characteristics with its safety profile, especially low frequency of hypoglycaemia and its acceptable efficacy on blood glucose lowering. Therefore many of physicians consider DPP-4 inhibitor is widely chosen as a monotherapy and one of combination therapy.

As for DPP-4 inhibitors administered on a daily basis, there are seven single ingredient drugs in this class and their dose-reduction manners are various in RI patients. Linagliptin and teneligliptin are not required dose reduction. On the other hand, other five drugs are recommended dose reduction or careful administration. Furthermore sitagliptin and alogliptin have four and three of drug formulations of different contained amount respectively in Japan. Japanese physicians are required proper use of complicated regimen in accordance with each patient's renal function.

Currently, there is no publication of actual situation on the prescription patterns of OADs and dose-reduction especially in DPP-4 inhibitors and other OADs needed to dose-reduction. However from viewpoint of appropriate use, relevant dose-reduction can contribute patients benefit. This study aims to assess the actual condition of dose selection of OADs among RI patients in Japan by using MDV database.

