9. RESEARCH METHODS

9.1 STUDY DESIGN

Study design:

- Descriptive cohort study

Comparison group

- OAD group, DPP-4 inhibitors group, SU group, BG group, TZD group, α -GI group, and Glinide group.

Strength of the study design

- Up-to-date information can be obtained and nationwide actual treatment status can be illustrated with using large-scale real-world database.

Analysis

- First analysis: type and dosage of drug prescribed for T2DM patients.
- [REDACTED]
- Main measures: number of patients, baseline characteristics at index month (age, sex), prior and concomitant use of glucose-lowering medications and insulin (type, dose), comorbidities (types and their percentages of patients), stage of RI defined by eGFR or serum creatinine value, glucose-lowering medications and their dosages (based on daily dose) for patients with RI, [REDACTED]
- [REDACTED]

Potential limitation

- The data held in MDV database is collected from DPC hospitals, not GP data. However they are including outpatient data because many of Japanese patients prefer to visit a hospital even though chronic disease.
- The rate of laboratory test data held in MDV database is limited. About 350,000 patients out of 2,600,000 patients (13.5%, April 2008 ~ April 2016) have laboratory data.
- The MDV database does not hold the time diagnosis of T2DM if it is out of study period. Therefore the onset date of diabetes or the first record of T2DM cannot obtain for all patients.
- The information on medication is based on prescribed record, not include adherence result. It means that exact dosage may not reveal actual dispensed prescription and dosage perfectly.
- Laboratory test date is not exactly matched with the index day of the first prescription of OAD. The sample size will have some impacts (reduction) to assure simultaneous timing of data. The latest lab result 30 days before the index date will be considered the status at the time of prescription
- All information of each patient is from consent given DPC hospitals. If patients have visits to other medical institutions, these data are not included in the MDV data.

- MDV database is composed of data from patients who hospitalized in DPC hospital so that more severe patient will be included in the database.

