9.2 SETTING

Medical Data Vision (MDV) clinical database is used.

Inclusion criteria

[figure not shown]
- Patients with T2DM (ICD code: E11 or E14).
- Patients must have their first prescription (defined as index date*) for any study drugs between 01/01/2014 and 30/09/2016.
- Patients must have at least 6 months enrolment verified by the presence of any record except for the study drug prescriptions within the database (look back period) prior to the index date for each drug.

Exclusion criteria

- Patients who were under 40 y.o. at the time of diagnosis of diabetes.
- Patients with record of type 1 diabetes mellitus (ICD code: E10).
- Patients who prescribed the study drugs during 6 month prior to index date for each drug.
- Patients whose mean visit interval are more than 92 days

*Index date is defined as follows:

- In case of comparing drugs within class, index date is defined as the date of first prescription for any study drugs as general name. Change of dosage is not counted as the index.
- In case of comparing drugs between class, index date is defined as the date of first prescription for study drug of class. Change of dosage is not counted as the index.

* The hospitalization period is not included in the mean visit interval.

Figure 1 Definition of Index data(date of first prescription for any study drugs)

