9.3.2 Outcomes

9.3.2.1 Primary outcomes

Outcome name: demographic and clinical characteristics of patients who had a prescription of OADs.

Time frame: on the index month

Safety issue: N/A

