9.7 DATA ANALYSIS

9.7.1 Main analysis

- For the primary objective, descriptive statistics of patients prescribed each compound and each class of OAD at least once will be presented for the baseline demographic and clinical characteristics:
 - Number of patients (n, % of total patients)
 - Age (mean ± SE, mean ± SD)
 - Sex
 - Concomitant medications (drug prescribed at index day) :
 - Use of biguanide (Yes/No)
 - Use of sulfonylurea (Yes/No)
 - Use of thiazolidinediones (Yes/No)

- Use of glinide (Yes/No)
- Use of α -GI (Yes/No)
- Use of GLP-1RA (Yes/No)
- Use of SGLT2 inhibitors (Yes/No)
- Use of insulin (Yes/No)
- Premedications (drug prescribed before index day):
 - Use of biguanide (Yes/No)
 - Use of sulfonylurea (Yes/No)
 - Use of thiazolidinediones (Yes/No)
 - Use of glinide (Yes/No)
 - Use of α -GI (Yes/No)
 - Use of GLP-1RA (Yes/No)
 - Use of SGLT2 inhibitors (Yes/No)
 - Use of insulin (Yes/No)
- Comorbidities:
 - Hypertension: Percentage of patients with a diagnosis of hypertension
 - Ischemic heart disease (IHD): Percentage of patients with a diagnosis of IHD
 - Myocardial Infarction (MI): Percentage of patients with a diagnosis of MI
 - Heart Failure (HF): Percentage of patients with a diagnosis of HF
 - Stroke: Percentage of patients with a diagnosis of stroke
 - Renal impairment: Percentage of patients with a diagnosis of renal impairment
 - Amputation: Percentage of patients with a diagnosis of amputation

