9.9 LIMITATIONS OF THE RESEARCH METHODS

- The data held in MDV database is collected from DPC hospitals, not GP data. However they are including outpatient data because many of Japanese patients prefer to visit a hospital even though chronic disease.
- The rate of laboratory test data held in MDV database is limited. About 350,000 patients out of 2,600,000 patients (13.5%, April 2008 ~ April 2016) have laboratory data.
- The MDV database does not hold the time diagnosis of T2DM if it is out of study period. Therefore the onset date of diabetes or the first record of T2DM cannot obtain for all patients.
- The information on medication is based on prescribed record, not include adherence result. It means that exact dosage may not reveal actual dispensed prescription and dosage perfectly.
- Laboratory test date is not exactly matched with the index day of the first prescription of OAD. The sample size will have some impacts (reduction) to assure simultaneous timing of data. The latest lab result 30 days before the index date will be considered the status at the time of prescription
- All information of each patient is from consent given DPC hospitals. If patients have visits to other medical institutions, these data are not included in the MDV data.
- MDV database is composed of data from patients who hospitalized in DPC hospital so that more severe patient will be included in the database.

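### Concomitant use is counted on the index day only, while the primary outcome is timed to the index month; an ongoing drug not renewed that day is recorded like a stopped one

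*Combined protocol and SAP*

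**What the plan says.** Section 9.7.1, and the Data analysis entry of the Abstract in the same terms, give two sets of Yes/No tables by glucose-lowering class. One is headed "Concomitant medications (drug prescribed at index day", the other "Premedications (drug prescribed before index day". Neither place has a days-of-supply, overlap or grace-period rule, or a rule that separates a premedication that continues from one that has ended.

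Other sections bear on the time window:

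- Section 9.3.2.1 sets the primary outcome, demographic and clinical characteristics, at "Time frame: on the index month".
- Section 9.1 lists "baseline characteristics at index month (age, sex), prior and concomitant use of glucose-lowering medications and insulin (type, dose". The month is attached to age and sex, and concomitant use follows with no window of its own.
- Section 9.2, for comparisons between classes, states that "index date is defined as the date of first prescription for study drug of class". The rule within a class works in the same way by generic name. A patient can therefore reach the index date already taking other glucose-lowering drugs.
- Section 9.2 excludes "Patients whose mean visit interval are more than 92 days", so mean intervals up to 92 days are allowed.
- Section 9.9 warns that "The information on medication is based on prescribed record, not include adherence result". It does not mention supply carried over from an earlier visit.

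**The concern.** A same-day rule records prescribing events, not drugs in use. If the index drug is started at a visit between renewals, the background drug has no record on that day although the patient is still taking it. The concomitant table then shows that class as absent.

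Concomitant use is one of the clinical characteristics that make up the primary outcome, and it is reported side by side for the drug groups named in section 9.1. If renewal timing differs between groups, the differences between columns are affected as well as the levels. A large database does not reduce this error. The background in section 7 also gives readers a reason to look at these tables for combination use, since it says physicians consider that "DPP-4 inhibitor is widely chosen as a monotherapy and one of combination therapy".

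**Working it through.** The plan gives no figure for concomitant use, renewal timing or supply length, so there is nothing to reproduce. The check is a comparison of definitions, followed by an illustration with assumed inputs.

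**1. What the tables record.** Take two patients, each with a biguanide prescription some weeks before the index date and none on it.

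| | Biguanide at index | Premedication | Concomitant |
|---|---|---|---|
| Patient A | still in supply, continues | Yes | No |
| Patient B | stopped | Yes | No |

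The records are identical. Cross-tabulating the two variables would not separate them either.

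**2. Size of the loss.** Let p be the true share of patients with ongoing co-use of a class, meaning started before the index date and still in use. Let u be the share of those not renewed on the index day. Then reported ongoing co-use = p × (1 − u), and the loss is p × u. Both inputs are assumptions.

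| p | u = 0 | u = 0.10 | u = 0.30 |
|---|---|---|---|
| 30% | 30% | 27% | 21% |
| 50% | 50% | 45% | 35% |
| 60% | 60% | 54% | 42% |
| 70% | 70% | 63% | 49% |

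For p = 60%: 0.60 × (1 − 0) = 0.60 and 0.60 × (1 − 0.30) = 0.42.

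The loss applies only to ongoing drugs. A drug first prescribed together with the index drug is always captured. If total co-use is 60% and only half of it (30%) is ongoing, u = 0.30 gives 0.60 − 0.30 × 0.30 = 0.51.

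**3. Does the index month resolve it?** Consider only a drug refilled every L days and out of step with the index visit, with the refill date equally likely on any day of the cycle. The chance of a prescription on the index day is 1/L. The chance of one in the same 30-day calendar month is about 30/L, up to 1.

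| L (days) | Index day | Index month |
|---|---|---|
| 30 | 1/30 = 3.3% | about 100% |
| 60 | 1/60 = 1.7% | about 50% |
| 92 | 1/92 = 1.1% | about 33% |

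These are not overall capture rates. They apply only to drugs that are out of step, and the documents do not say how many are. They show that the two windows give different counts, and that the month would reduce the loss without removing it. The month also admits the opposite error: a drug prescribed early in the month and replaced on the index date would count as concomitant.

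**The case against.** The strongest reply is that same-day prescribing is an explicit, reproducible rule in a descriptive study with no hypothesis testing, and that nothing shows it to be wrong often. The index date is itself a prescribing visit, and background drugs may usually be renewed then. The 92-day criterion caps the mean interval between visits; it says nothing about supply length or refill timing. An ongoing drug is not lost, because it still appears under premedication. An overlap rule would rest on a days-of-supply field that the protocol does not mention, and it would count some drugs being replaced as concomitant.

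Much of this stands. The size is unknown and may be near zero, and the alternative rule has its own error. What remains is that the stated rule cannot tell a continuing drug from a stopped one, that the plan names two different time windows, and that section 9.9 does not mention the issue.

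Two stronger readings are tempting:

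- **A reader might infer that the study will misreport monotherapy, add-on and switch rates.** The visible plan defines no such category, and some objectives and analyses are redacted. The documents support only misclassification in the Yes/No tables and in how they are read.
- **A reader might infer that concomitant use can only be under-counted.** That holds for carried-over supply alone. A drug prescribed on the index day and stopped soon after counts as concomitant, and the database includes inpatients, whose use may be temporary.

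**Conclusion.** The point holds as a definitional weakness that should be corrected before the analysis. The same-day rule in the Abstract and section 9.7.1 does not match the index-month time frame in section 9.3.2.1. It also records an ongoing drug that is not renewed on the index day exactly as it records a stopped drug.

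Through this mechanism reported concomitant use falls by p × u. With an assumed p of 60% and u from 0% to 30%, the loss is 0 to 18 percentage points. Nothing in the documents locates the true value within or beyond that range.

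The conclusion assumes that the six-month exclusion in section 9.2 applies to the index drug or class only, as the premedication tables imply. If it barred every study drug in those six months, the mechanism would be largely confined to the tabulated classes outside the section 9.3.1 list: GLP-1 receptor agonists, SGLT2 inhibitors and insulin.

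**What to change.** 1. Reconcile index day with index month in the Abstract and sections 9.1, 9.3.2.1 and 9.7.1, and state one window for concomitant use.
2. Count a glucose-lowering drug as concomitant if it is prescribed on the index date, or if an earlier prescription's days of supply cover that date. State any grace period.
3. Keep the same-day count as a second column.
4. If days of supply are not in the extract, use a fixed window instead. For example, count a drug prescribed on the index date, or one prescribed within 92 days before it and again within 92 days on or after it. State the limitation in section 9.9.

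The cost is a little programming, plus confirmation that the supply field exists, which is an assumption here. The downside is that some drugs being replaced will count as concomitant. The gap between the two columns is an upper bound on how many the wider rule adds.

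The 92-day look-back in the fallback fits within the six months of enrolment already required. The forward part does not fit for late entrants: July, August and September 2016 make 31 + 31 + 30 = 92 days, so index dates after 30 June 2016 lack a full window unless the extract runs past 30 September 2016. Those patients should be flagged or shown separately.

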9.5 STUDY SIZE

All available data from 01/01/2014 to 30/09/2016 will be included to ensure the maximum number of patient.

All patients with a prescription of OADs and DPP-4 inhibitors from 01/01/2014 to 31/08/2015 and a diagnosis of T2DM is estimated that approximately 9,890 and 7,579 patients respectively have been prescribed a study drug in the MDV database to be included in the study.

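### Premedication has no start of window, so its percentage rises with each patient's visible history and comparability between drugs is not assured

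*Combined protocol and SAP*

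**What the plan says.** The Abstract and Section 9.7.1 give the same definition: "Premedications (drug prescribed before index day"). Eight yes/no rows follow: biguanide, sulfonylurea, thiazolidinedione, glinide, α-GI, GLP-1RA, SGLT2 inhibitor and insulin. Section 9.3.3 lists prior use as a covariate, identified by ATC code and drug name, and gives no period.

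Section 9.2 has two 6-month rules, and both concern eligibility. The first is a minimum enrolment: "Patients must have at least 6 months enrolment verified by the presence of any record except for the study drug prescriptions within the database". The second is a washout, which excludes "Patients who prescribed the study drugs during 6 month prior to index date for each drug".

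The index date depends on the table. For compounds: "In case of comparing drugs within class, index date is defined as the date of first prescription for any study drugs as general name". For classes: "In case of comparing drugs between class, index date is defined as the date of first prescription for study drug of class". Section 9.1 names seven comparison groups, and Section 9.7.1 presents the characteristics by compound and by class.

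**The concern.** A yes/no count of any earlier prescription can only rise as more history becomes visible. The enrolment rule sets a floor of 6 months and no ceiling, so patients contribute unequal look-back. A drug stopped two years before index counts the same as one stopped last month, but only in patients whose records reach back that far.

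The tables set compounds and classes side by side. One patient can enter several groups, each with its own index date, and in that patient a drug started later has more visible history behind it. If typical history differs between groups, part of a difference in premedication would reflect record length and not prescribing. Premedication belongs to the primary outcome, and the limitations in Section 9.9 do not mention unequal look-back.

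**Working it through.** The plan states no premedication figure, so there is none to reproduce. The check has four steps.

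**1. Is a window given anywhere in the visible text?**

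| Place | Item | Window |
|---|---|---|
| Abstract; 9.7.1 | Premedication | Before index day, no start |
| 9.3.3 | Prior use | None |
| 9.2 | Enrolment | At least 6 months (eligibility) |
| 9.2 | Washout | 6 months (exclusion) |
| 9.3.2.1 | Primary outcome time frame | Index month, not usable as a look-back for past drugs |
| 9.7.1 | Concomitant drugs | Index day |
| 9.3.3 | Serum creatinine | 6 months |

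Other baseline items have a defined time point or window. Premedication has only an end.

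**2. How far can visible history vary?** The floor is 6 months. Section 9.5 says "All available data from 01/01/2014 to 30/09/2016 will be included to ensure the maximum number of patient". If history starts on 01/01/2014, the longest possible look-back is 01/01/2014 to 30/09/2016: 1,003 days / 30.4375 = 33.0 months. The earliest index date with 6 months behind it is then about July 2014. Yet Section 9.2 accepts index dates from 01/01/2014, and 6 months of look-back for those needs records from 2013. So the start of history is itself unclear, and 33 months is the upper end only under that assumption.

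**3. What does that do to one patient's chance of being counted?** Let r be the chance per visible month of a prior prescription of a given class, and W the months of history. The values r = 1% and 2% are assumptions, not document figures.

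P(W) = 1 − (1 − r)^W

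| | W = 6 | W = 33 |
|---|---|---|
| r = 1% | 1 − 0.99^6 = 5.9% | 1 − 0.99^33 = 28.2% |
| r = 2% | 1 − 0.98^6 = 11.4% | 1 − 0.98^33 = 48.7% |

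Continuing users are found in any window. If a share p0 = 20% (assumed) are continuing users, P(W) = p0 + (1 − p0)[1 − (1 − r)^W]. At r = 1% this gives 0.20 + 0.80 × 0.059 = 24.7% at 6 months and 0.20 + 0.80 × 0.282 = 42.6% at 33 months. The gap falls from about 22 to about 18 points, and the relative effect is much smaller.

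These figures contrast two extreme patients. A drug group mixes index dates and record lengths, so they do not estimate a difference between drugs. With W fixed at 6 for everyone, the result is 5.9% or 11.4% however long the record is.

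**4. How does a 6-month window meet the washout?** They cover the same period.
- If the washout is specific to the index class, the own-class row of a class table is 0% by construction.
- If it is specific to the index compound, that compound contributes nothing to its class row in a compound table.
- If it covers every listed OAD, the biguanide, sulfonylurea, thiazolidinedione, glinide and α-GI rows are all 0%: five of the eight.

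Under the present definition the own-drug or own-class entry can come only from history beyond the guaranteed 6 months, where look-back is unequal.

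**The case against.** A reader might infer that premedication percentages simply are not comparable between drugs, or that drugs with later first prescriptions will show more of it. The documents do not support either statement. Distortion between groups requires history length to differ between groups, and no such lengths are given. Section 8 limits the research question to OADs that could be prescribed during the whole study period, and all groups draw index dates from the same 33 months. History also depends on when each patient's records begin, not on the index date alone.

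A reader might also infer that look-back extends to 2008 from the statement in Section 9.9 that "About 350,000 patients out of 2,600,000 patients (13.5%, April 2008 ~ April 2016) have laboratory data". That period describes the laboratory-data count, not the extract for this study, so no figure here rests on it.

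Three further points have weight. Any recorded prior use is a legitimate description of treatment history, and the study tests no hypothesis. Section 9.2 labels the enrolment period as a look-back period, which may have been meant as the baseline window; but it is worded as a minimum, so it does not fix one. Finally, Figure 1 is not shown and parts of the analysis text are redacted, so a window could be stated there; the visible definition, given twice, has none.

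The objection that a plain 6-month filter would leave structurally empty rows is correct, and the fix has to deal with it.

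**Conclusion.** The point holds in limited form. As written, the premedication percentage depends on how much history is visible, and only 6 months is guaranteed. Comparability between compounds and classes is therefore not assured. Whether it is actually lost, by how much and in which direction, cannot be determined from the documents.

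The 6-11% versus 28-49% contrast shows only how sensitive one patient's classification is. It assumes a 1-2% monthly chance, no continuing users and history starting on 01/01/2014. No error rate or study size is affected. The item belongs to the primary descriptive tables, so the definition should be settled before they are programmed.

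**What to change.** - Report premedication for other OAD classes, GLP-1RA, SGLT2 inhibitors and insulin in one window common to all patients: the 6 months before the index day, index day excluded.
- Keep use at any time before index as a supplementary row.
- Show the distribution of look-back length by drug or class, and state the date from which records are searched.
- State that the washout is specific to the index drug (compound tables) or index class (class tables). In the 6-month table, mark the own-drug or own-class entry as not applicable. Where a compound table keeps its class row, label it as other compounds of that class.

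The cost is a date filter, one extra row per class, a short look-back table and a clarified washout sentence. It needs no new data and loses no patients. The downside is that drugs stopped more than 6 months before index leave the main rows and appear only in the supplementary one, which still depends on record length and should be footnoted accordingly.

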Protocol date: 09 February 2017	Study number: 1218.178	Version/Revision: 1.0	Version/Revision date:
		
01/01/2014 to 31/08/2015 and a diagnosis of T2DM is estimated that approximately 9,890 and 7,579 patients respectively have been prescribed a study drug in the MDV database to be included in the study.
 
The power calculation has not been conducted as there will not be any hypothesis testing in the analysis. Data of MDV is from all DPC hospitals. Data is collected directly from hospitals, so it holds every data of all insurances.
 
Limitaion: Number of hospitals providing with lab test results are limited.
	
Data analysis:	
 • For the 1st objective, descriptive statistics of each compound and each class of OAD will be presented for the baseline demographic and clinical characteristics: 
 • Number of patients • Age (mean ± SE, mean ± SD) • Concomitant medications (drug prescribed at index day) : 
 • Use of biguanide (Yes/No) • Use of sulfonylurea (Yes/No) • Use of thiazolidinediones (Yes/No) • Use of glinide (Yes/No) • Use of α-GI (Yes/No) • Use of GLP-1RA (Yes/No) • Use of SGLT2 inhibitors (Yes/No) • Use of insulin (Yes/No) • Premedications (drug prescribed before index day): 
 • Use of biguanide (Yes/No) • Use of sulfonylurea (Yes/No) • Use of thiazolidinediones (Yes/No) • Use of glinide (Yes/No) • Use of α-GI (Yes/No) • Use of GLP-1RA (Yes/No) • Use of SGLT2 inhibitors (Yes/No) 		

Proprietary confidential information © 2017 Boehringer Ingelheim International GmbH or one or more of its affiliated companies

Name of company: Boehringer Ingelheim			
Name of finished medicinal product: If applicable, list centrally-authorized medicinal product(s) subject to the study.		Trazenta	
Name of active ingredient: List pharmacotherapeutic group(s){ACT codes} and active substance(s) subject to the study		A10N,A10H,A10J,A10K,A10L A10M	
Protocol date: 09 February 2017	Study number: 1218.178	Version/Revision: 1.0	Version/Revision date:

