MDV provides commercial claims database for inpatient and outpatient consisting medical records from more than 12.94 million patients from 230 large acute care DPC hospitals as of Feb 2016. According to the data released by the company in Sept 2016 [1], in one year period between July 2015 and June 2016, cumulative number of patients in the claims database was 7,546,862 patients. 82% of patients (6,152,732) were associated with outpatient claims only, while 15% of patients (1,131,869) had claims from both in and out-patient care. Only 3% of patients (262,261) had exclusively in-patient claims. Laboratory data is available for approximately 10% of patients contained in the database. The DPC is a case-mix system, similar to Medicare in the US. It comprises of 18 Major Diagnosis Categories, 520 diagnostic groups and 2,658 case-mix groups. In the DPC algorithm, the diagnosis, procedure and comorbidities/complications are the 3 key variables for classification. The diagnosis and comorbidities/complications are coded using the ICD10 scheme, while the procedures are coded using the Japanese Procedure Codes. Not only administrative claims data but also

detailed patient data are collected for all the inpatients discharged from the participating hospitals.

[figure not shown]

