9.3.3 Covariates

Age at index date

Sex

Prior and concomitant use of glucose-lowering medications and insulin (type, dose): drug name was defined by ATC code and drug name.

Comorbidities (types and their percentages of patients): defined by ICD-10 code

Stage of RI: defined by eGFR or serum creatinine value (See [Annex 3](#)).

eGFR is calculated using serum creatinine, age, and sex as follows (formula for Japanese):

The latest serum creatinine value within 6 months from index date will be used.

*where Cr is serum creatinine (mg/dL), age is the age at index date.

- eGFR formula*:

$$\text{eGFR (mL/min/1.73m}^2\text{)} = 194 \times \text{Cr}^{-1.094} \times \text{age (year)}^{-0.287} (\times 0.739 \text{ if female})$$

*The formula recommended by the Japanese Society of Nephrology in clinical practice in Japan is the above formula calculated from three data of serum creatinine, age and sex.

<References>

- (Japanese) Evidence-based Clinical Practice Guideline for CKD 2013 (the Japanese Society of Nephrology)
URL (accessed on 1st Feb, 2017):
http://www.jsn.or.jp/guideline/pdf/CKD_evidence2013/all.pdf
- (English) Japanese Society of Nephrology. Clin Exp Nephrol 2014;18: 346.

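### Amputation is identified by ICD-10 diagnosis alone, so operations recorded only under a procedure code would be missed and the percentage may be under-counted by an unknown amount

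*Combined protocol and SAP*

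**What the plan says.** Section 9.7.1 lists seven comorbidities to be described for each compound and each class: hypertension, ischemic heart disease, myocardial infarction, heart failure, stroke, renal impairment and amputation. The last is given as "Amputation: Percentage of patients with a diagnosis of amputation", and the data-analysis part of the abstract (section 4) words it the same way.

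Section 9.3.3 sets the rule for the whole group: "Comorbidities (types and their percentages of patients): defined by ICD-10 code". No code list follows, for amputation or for any other comorbidity.

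Section 7 describes how the hospital case-mix (DPC) system behind the database is coded: "The diagnosis and comorbidities/complications are coded using the ICD10 scheme, while the procedures are coded using the Japanese Procedure Codes". It also says that "the diagnosis, procedure and comorbidities/complications are the 3 key variables for classification".

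The time frame for the primary outcome, which includes clinical characteristics, is in section 9.3.2.1: "Time frame: on the index month". No separate look-back is given for comorbidities.

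**The concern.** Six of the seven rows are conditions that a diagnosis code names directly. Amputation is an operation. By the plan's own account, operations are recorded in a coding system that the comorbidity definition does not use. A patient whose amputation appears only as a procedure record would be counted as not having had one.

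The limitations in sections 9.1 and 9.9 and the bias statement in section 9.12 do not mention this. A reader of the report could take the row as the share of patients with an amputation, when it is the share with a recorded diagnosis of one. The row belongs to the primary-objective description and is shown by compound and by class. The counts in each cell will be small, and a few missed cases could matter in relative terms.

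**Working it through.** The plan states no amputation rate, no validity figure for the diagnosis code and no precision target for this row, so there is no figure to reproduce. The check has two parts: what follows from the text, and an illustration under stated assumptions.

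**What follows from the text**

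1. The count uses ICD-10 records only (sections 9.3.3 and 9.7.1).
2. Procedures are coded outside ICD-10 (section 7).
3. Patients counted by diagnosis or procedure include all those counted by diagnosis. Adding procedure codes can raise the count or leave it unchanged, but cannot lower it.
4. The diagnosis-only percentage is therefore equal to or below the combined one. It is strictly below only if at least one patient has a procedure record without a qualifying diagnosis.

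**Illustration**

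- N = 9,890, the estimated number of patients on oral antidiabetic drugs in section 9.5. It covers prescriptions to 31/08/2015 only and serves here just to turn percentages into patients.
- p = percentage with an amputation by diagnosis or procedure: 0.2% to 1.0% (assumed).
- s = share of those patients with a qualifying ICD-10 record: 0.3 to 1.0 (assumed; the upper end is the case of no loss).
- f = share of patients without an amputation who carry the diagnosis in error: first set to 0.

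Diagnosis-only percentage = p × s + (1 − p) × f. With f = 0, the shortfall is p × (1 − s).

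| p | s | Diagnosis-only | Patients, diagnosis-only / combined | Shortfall (percentage points) |
|---|---|---|---|---|
| 0.2% | 0.3 | 0.06% | 6 / 20 | 0.14 |
| 0.5% | 0.3 | 0.15% | 15 / 49 | 0.35 |
| 0.5% | 0.5 | 0.25% | 25 / 49 | 0.25 |
| 0.5% | 0.9 | 0.45% | 45 / 49 | 0.05 |
| 0.5% | 1.0 | 0.50% | 49 / 49 | 0.00 |
| 1.0% | 0.3 | 0.30% | 30 / 99 | 0.70 |

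For example, at p = 0.5% and s = 0.5: 0.005 × 0.5 = 0.0025, and 9,890 × 0.0025 = 24.7, or about 25 patients, against 9,890 × 0.005 = 49.

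**Direction against the truth**

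Diagnoses recorded in error push the other way. The shortfall is cancelled when f = p(1 − s)/(1 − p). At p = 0.5% and s = 0.5 this is 0.0025/0.995 = 0.251%, about 25 patients. So the direction is certain against a combined definition, but not against the true percentage.

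**The case against.** The strongest reply is that the plan uses the coding system that section 7 assigns to this kind of variable. Amputation is listed as a comorbidity, comorbidities are coded in ICD-10, and the row is labelled as a diagnosis, so it reports what it says. As no code list is given, nobody can show that the chosen codes would miss past amputations. This stands against calling ICD-10 the wrong system. It does not close the gap, because a procedure-only case is still missed and the text does not say so.

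Procedure codes also have a blind spot. Sections 9.1, 9.9 and 9.12 already disclose that care at other institutions is not in the database. For an amputation performed elsewhere, a later diagnosis may be the only trace. This stands: procedure codes can supplement the ICD-10 definition but should not replace it.

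It is also unconfirmed that the study holds procedure fields. Section 9.6 says that csv files were supplied without naming their contents, and the variables in section 9.3 include no procedures. Section 7 shows that procedures are coded in the source system, not that they are in this extract. This stands as a condition on the fix.

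Finally, the consequence is small. The abstract says "The power calculation has not been conducted as there will not be any hypothesis testing in the analysis", and the readable text does not use amputation in eligibility, index date or renal staging. This stands in full.

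A reader might go further and infer that the reported percentage will be too low. The documents do not support that. They do not say how often an amputation lacks an ICD-10 record, the loss is zero if every amputee has one, and false-positive diagnoses could offset it.

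**Conclusion.** The concern holds in a limited form. Amputation is ascertained by diagnosis only, the plan describes a second coding system where the operation itself would be recorded, and nothing in the text uses that system or discloses the omission. The percentage may be under-counted.

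The amount cannot be derived from the documents. The illustrative range of 0 to 0.70 percentage points rests wholly on assumed values of p and s and on no false-positive diagnoses. It shows scale only.

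This is a minor point: one of seven descriptive comorbidity rows, with no test, sample size or error rate depending on it. It is worth making because the remedy is cheap and the definition is better settled before analysis, which section 6 schedules to start on 1 March 2017.

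**What to change.** In sections 9.3.3 and 9.7.1, and in the matching line of the abstract:

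- Define amputation as an ICD-10 amputation record or a Japanese Procedure Code for amputation, and list both sets of codes.
- Apply the same look-back window as for the other comorbidities, and state that window. The plan now gives only the index month, so a different window for amputation alone would be a separate change.
- Report the diagnosis-only count beside the combined count, so that the effect of adding procedure codes is visible.
- Note in section 9.9 that operations at non-contributing hospitals are still not captured by procedure code.

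The cost is one extra code list and confirmation that procedure fields are in the data extract. If they are not, keep the diagnosis-only definition, list its ICD-10 codes and state diagnosis-only ascertainment as a limitation.
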